## **I. Objective**

The vast majority of primary and behavioral health care services are provided by solo or small practices, yet to date collaborative chronic care models (CCM) have not been implemented in these settings. Mood disorders are common and represent the most expensive mental disorders for commercial health plans and employers. The goal of this study is to implement and test a CCM for mood disorders for solo and smaller practices in partnership with Aetna Health Plan, with an eye towards making the business case and demonstrating value for CCMs for these settings that can reach patients wherever they receive treatment.

## **II. Specific Aims/Hypotheses**

A 2010 HHS report highlighted the prevalence, morbidity, and cost associated with clusters of co-occurring chronic conditions, both physical and mental. The report also underscored the lack of sustainable treatment strategies for these afflicted individuals, and the difficulties in customizing patient-centered interventions.

Collaborative chronic care models (**CCMs**) are effective in treating chronic medical and mental illnesses at little to no net healthcare cost. To date CCMs have primarily been implemented at the facility level and primarily developed for and adopted by larger healthcare organizations. However, we have determined that the vast majority of primary care and behavioral health practices providing commercially insured care are far too small to implement such models. Health plan-level CCMs can address this unmet need.

Chronic mood disorders (e.g., bipolar disorders, depression) are common and are associated with extensive functional impairment, medical comorbidity, and personal and societal costs. While unipolar depression is more common, bipolar disorder is more costly on a per patient basis due to its chronic and severe nature. Moreover, bipolar disorder is the most expensive mental disorder for U.S. commercial health plans and employers. While evidence-based care parameters have been well established for mood disorders, quality of care and health outcomes in general mental health practice are suboptimal. The majority of these patients suffer from clusters of comorbid conditions, both physical and mental. Thus mood disorders represent optimal tracer conditions with which to improve management strategies for individuals with multiple chronic conditions.

Accordingly, we have partnered with Aetna Inc. to develop and implement a CCM designed to improve outcomes for persons with mood disorders for solo or small practices, with an eye towards developing a business case for a generalizable plan-level CCM for chronic disorders. We will conduct an RCT of a health plan-level CCM vs. education control. The population of interest will be Aetna beneficiaries across the country hospitalized for depression or bipolar disorder treated in solo or small primary care or behavioral health practices. Patients will be randomized to one year of outpatient treatment augmented by the CCM or education control, for a total of 344 participants. CCM care management will be fully remote from practice venues and patients, implemented by existing providers (the Aetna care management center). A business case will be developed using the Replicating Effective Programs (**REP**) strategy that identifies generalizable facilitators for CCM spread and value added of CCMs to be vetted to key industry and policy stakeholders.

### **Our Specific Aims are to:**

1. Determine whether individuals with mood disorders treated with a health plan-level CCM demonstrate improved health outcomes and quality of care at 12 months compared to those who are mailed educational material alone (Educational Control-EC).

Our **primary hypothesis** is that compared to EC, the mood CCM will result in a) reduced mood symptoms in 12 months, or b) improved health-related quality of life.

Our secondary hypotheses is that patients receiving CCM vs. EC will have improved guideline-concordant care (e.g., mood disorders treatment, cardiometabolic monitoring), reduced hospitalizations, and improved work productivity within 12 months.

2. To support subsequent CCM dissemination by identifying key organizational, provider, and patient characteristics associated with CCM engagement and outcomes.
3. To conduct a cost-effectiveness analysis of CCM versus EC on changes in patient utilities over 24 months and apply findings to develop a business case for CCMs in smaller practices.

This proposed R18 addresses **AHRQ's research demonstration and dissemination priorities**, particularly around prevention and care management, with an emphasis on vulnerable groups including more rural populations (the majority of Aetna enrollees are seen in smaller practices). It also confronts unanswered organizational and financial questions raised by a recent **AHRQ report** ("A National Agenda for Research on Collaborative Care"). As one of the first cross-diagnosis CCM-based implementation studies focused on small practices, this groundbreaking study is informed by an extensive partnership with a network-model health plan (Aetna). The study also applies a novel implementation framework (REP) in which the CCM is delivered by existing providers. In addition to the specific importance of this practice-research partnership to further implement CCMs among small practices at the health plan level within a natural experiment setting, this study will contribute to the evolution of the business case for CCMs in general, enhance the utility of plan-level panel management focused on vulnerable populations across different treatment settings, and inform remote technologies that will facilitate emerging healthcare initiatives (e.g., accountable care organizations, health IT).

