##### **2. Mood disorders are common exemplars for complex patients at high risk in need of CCMs.**

Mood disorders (depression and bipolar disorder) are chronic illnesses associated with substantial social dysfunction (23) and rank in the top ten causes of disability worldwide (24). National studies of the U.S. population estimate the lifetime prevalence for bipolar spectrum disorders as 6.4% (25, 26) and 16.6% for major depressive disorder (27). Medical comorbidity is the rule for mood disorders, in which the majority of patients suffer from at least one co-occurring chronic medical illness (28, 29). Persons with mood disorders die younger, mainly from cardiovascular disease (30-32). Quality of care is suboptimal for both chronic medical (33) and mental (34-41) disorders, underscoring the need for coordinated, comprehensive care. Not

surprisingly, the recently released IOM comparative effectiveness priority list includes among its top-quartile priorities research on comprehensive care coordination for chronic diseases (42). While unipolar depression is more common, patients with bipolar disorder incur the most health care costs of any mental illness (43). Up to 70% of direct treatment costs for mood disorders are generated outside the mental health sector, notably in primary care (44-46). In response to extremely high costs and high disease burden associated with mood disorders, Aetna has partnered with us to develop and implement care management methods for this group.

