**CM and study staff handling of suicide risk/adverse events:** Imminent risk (suicidal or assaultive ideation, significant medication toxicity) are managed via protocols used in prior studies (8, 50, 52). In the pilot study (Section C.3), care managers identified 4 out of 457 who had suicidal ideation and, through established protocols, alerted the provider and arranged emergency evaluation; no suicide attempts occurred during the pilot study. Moreover, CCMs have been shown to reduce suicide (94). Study staff (both University of Michigan and Aetna) will be trained to identify and address suicidal ideation in patients. If the patient articulates thoughts of death or suicidal ideation, the study team member will ask the patient to elaborate on recent suicidal behavior (i.e., ask if he or she has an active plan). Follow-up regarding the situation will be based on the patient's responses and whether the study team member perceives that the patient is in immediate danger (e.g., active plan verbalized). Endorsement of the suicidal thoughts on the survey will also serve as an emergent/urgent situation. The study team member will then ask whether there is another individual with the patient (if over the phone), and will remain on the phone while instructing the other individual to get help. If no one else is present with the patient, the team member direct the patient to his/her local emergency room or, refer to a national suicide hotline that can do further assessment and planning, so the patient can get immediate help. Adverse event reporting is outlined further in the data safety monitoring plan. We will have a adverse events and serious adverse events management plan for this project, as due to the nature of this population, fairly frequent visits to the emergency room that do not require hospitalization and hospitalizations due to their mood disorder exacerbation are to be expected. All adverse events encountered by both University of Michigan and Aetna staff will be reported to the UM IRB according to our management plan (see Data Safety Monitoring Plan document).

**C.5.d. Interventions: EC and CCM.** The **education control (EC) condition** consists of a self-guided workbook mailed to patients developed by study investigators (95) along with standard care from the practice, but none of the CCM components from the plan-level CM.

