**Training** for care managers will follow existing Aetna standard procedures for telephonic and web-based training. This will consist of 16 hours of telephonic training by [name] and her study team over 2 weeks modeled after our current on-site training package.

**Technical assistance** will be provided by the Joint Operating Committee and supported by study consultants [name] (telephonic care management) and [name] (implementation processes). Joint Operating Committee members will conduct conference calls with the care managers (weekly) and supervisors (monthly) to guide the use of CCM components, particularly with regard to interface issues between: care managers and patients; care manager and providers/practices; and patients and providers. The Joint Operating Committee will have separate quarterly and ad hoc calls with consultants for debriefing and advice.

**C.5.f. Data Collection and Measures.** Key outcomes data will be ascertained from patients (including surveys, medical record- eTUMS reviews, and claims data) and organizational surveys (Table 5).

**Patient survey:** A concise (15-30 minute) quantitative survey will be collected from patients via phone at baseline, 6, 12, 18, and 24 months thereafter by the research associate (RA). If the RA is unable to reach the patient via phone for follow-up assessments after multiple attempts, a survey will be mailed to the confirmed last known address of the participant as a final attempt to receive this data. Patients will be asked to return this survey without any identifying information on the survey or the envelope. The survey will contain a subject ID number to identify the patient’s survey when it is returned via mail. Patient outcomes data will be entered by the RA into a database on a password-protected research computer within a secure network server at the University of Michigan.

**Patient utilization and cost data,** described below will be ascertained from the Aetna eTUMS and claims databases, and exported securely for merging with survey data and analysis at the University of Michigan.

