Missing Data: We attained subject retention of 80% over a three-year follow-up in one study (50, 51), and recent 1-year data (MH0745409) indicate 90% retention. Extent and pattern of missingness will be examined for outcome variables as well as for baseline covariates. We expect missingness to be completely at random or at random, in which case the proposed analytical methods will give unbiased estimates of treatment comparison. We will examine how sensitive our conclusions are to potential non-ignorable missingness using a pattern mixture model that will allow us to either model the observed pattern of missingness or change the imputations to represent the likely differences in conditional distributions between observed and missing data (128, 129). For the latter, we will combine the results from each imputed data using Rubin's rules (130).

**Aim 1 primary outcomes (H1a: symptoms, quality of life):** Primary outcomes are continuous, and based on pilot data, are expected to be normally distributed. If a continuous outcome exhibits a significant lack of normality, other options will be considered including data transformation, categorization, and non-parametric analyses. Four linear mixed-effects models accounting for clustering will be run to assess the CCM effects compared to EC on changes in PHQ-9, ISS, and SF-12 PCS and MCS scores over 12-months, adding baseline values of the outcome measure, the effect of CCM, time, and CCM X time interaction.

**Aim 1 secondary analyses:** For guideline concordance and hospitalization, we will compare the likelihood of receiving the guideline-concordant treatment over 12 months (Table 5) as well as the likelihood of an ambulatory care sensitive admission using a generalized linear mixed-effects model (GLM) with logit link. Similar to our primary hypotheses, linear mixed-effects models will be conducted to determine the effect of CCM vs. EC on changes in the Work and Social Adjustment Scale.

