**Aim 2 analyses are considered exploratory** but will be used to gain insight into the mechanisms by which CCM impacts patient outcomes. We will first explore the strength and direction of the association between patient-level CCM engagement (API-D scores- see section C.5.f) (119) on changes in outcomes (SF-12, PHQ-9 and ISS scores) by adding patient-level API-D scores to the aforementioned linear mixed-effects models from Aim 1. We will also be run exploratory analyses in which we add key organizational factors (e.g., non-solo practice, practice type-primary care vs. behavioral health, presence of non-MD clinical staff, EMR use, ownership), and other patient factors (e.g., demographics, comorbidities) in the models specified in Aim 1. In secondary analyses we will also incorporate the number of additional optional sessions covering supplemental modules completed by the patient (Section C.5.d).

**Aim 3: Both a payer and societal-based cost-effectiveness analysis (CEA) will be conducted.** A CEA from the payer perspective will involve comparison of utilization costs of health service providers including CM's time ascertained from time-motion survey. A societal perspective will add non-health care costs incurred by patients including time and transportation. Generalized Linear Models with log link functions will be used to correct for heteroscedasticity and reduce the impact of outliers (131). The incremental effectiveness of CCM compared to EC will be measured by changes in health utilities, assessed using a method described by Zivin (132) and Brazier (133) which translates six of the SF-12 items to changes in health utility (SF-6) based on responses to standard gamble questions given by community members regarding all combinations of possible health states. Cost-effectiveness ratios will be calculated based on the difference in per patient costs and effectiveness of CCM versus EC. To quantify uncertainty around these ratios, a standard nonparametric

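### Aim 3 gives death no utility value: under the plan's only missing-data rule, a patient who dies is omitted or valued like a living patient

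*Combined protocol and SAP*

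**What the plan says.** Section II gives Aim 3 as: "To conduct a cost-effectiveness analysis of CCM versus EC on changes in patient utilities over 24 months". The Aim 3 paragraph of C.5.g repeats the measure: "The incremental effectiveness of CCM compared to EC will be measured by changes in health utilities". No life-years, QALYs or survival term is mentioned.

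The utilities are derived from six SF-12 items (C.5.g and Table 5). C.5.f gives the schedule: a "quantitative survey will be collected from patients via phone at baseline, 6, 12, 18, and 24 months", with a mailed form as a last resort.

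The Missing Data paragraph of C.5.g is the only rule for an absent value. It states: "We expect missingness to be completely at random or at random". It then adds: "We will examine how sensitive our conclusions are to potential non-ignorable missingness using a pattern mixture model". That model may change the imputed values to reflect likely differences between observed and missing data. The paragraph does not mention death and is not tied to Aim 3.

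On costs, C.5.h counts only utilization within the plan. C.5.g forms the ratio from per-patient differences in cost and effect and bootstraps it. Nothing separates death from disenrolment or loss to follow-up. The limitations section (C.5.j) calls the cost-effectiveness analysis exploratory and not fully powered.

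**The concern.** A patient who dies returns no further surveys, but their later utility is not unknown. On a utility scale anchored at death it is 0. An at-random model supplies, explicitly or through the likelihood, a value typical of comparable living patients. A complete-case analysis omits the patient. Either way the death costs its arm nothing in effectiveness.

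The plan itself makes mortality relevant. Section III.A.2 says: "Persons with mood disorders die younger, mainly from cardiovascular disease". The suicide-risk paragraph of C.5.c says that models of this kind have been shown to reduce suicide. Patients are enrolled after a psychiatric hospitalization. If CCM did prevent deaths, the effect measure would not register it. If CCM happened to have more deaths, the measure would not register that either. The incremental effect feeds the cost-effectiveness ratio and, through C.5.h and Table 6, the business case and reimbursement proposals.

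**Working it through.** **Inputs from the plan.** 172 patients per arm (C.5.i), 24-month horizon, surveys every 6 months. The plan gives no mortality rate, utility level, utility SD or expected utility gain, so each of these is an assumption below.

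**The plan's own figure.** C.5.i uses d = 0.36, two-sided 0.05, 90% power, ICC 0.05 and 2 patients per practice. Two-sample n = 163 per arm. The design effect is 1 + (2 - 1) × 0.05 = 1.05, and 163 × 1.05 = 171.2, giving 86 practices or 172 patients per arm. The figure reproduces before any dropout allowance. It is a primary-aim size, used here only as the number randomized per arm. There is no Aim 3 figure to reproduce.

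**Shift per excess death, 24-month utility.** With utility u when alive, scoring a death as 0 lowers the arm mean by u/172.
- u = 0.6: 0.6/172 = 0.0035
- u = 0.7: 0.7/172 = 0.0041
- Share of an assumed gain of 0.04: 0.0035/0.04 = 9% to 0.0041/0.04 = 10%
- Share of an assumed gain of 0.02: 0.0035/0.02 = 17% to 0.0041/0.02 = 20%

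**Shift per excess death, QALYs.** A death at month 12 loses one year at u, again u × 1/172 = 0.0035-0.0041. A gain of 0.02-0.04 held for two years is 0.04-0.08 QALYs. The share runs from 0.0035/0.08 = 4% to 0.0041/0.04 = 10%, roughly half the endpoint figure.

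**Equal deaths.** With d deaths in each arm and gain g, scoring death as 0 changes the difference by only d × g/172. For d = 2 this is 2 × 0.02/172 = 0.0002 to 2 × 0.04/172 = 0.0005.

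**How likely is an imbalance?** Assume 24-month mortality of 0.5-3%, equal in both arms, with independent binomial counts. Expected deaths per arm are 172 × 0.005 = 0.9 to 172 × 0.03 = 5.2. The chance that the arms differ by at least one death is 66-87%, and by at least two 22-63%.

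**Against sampling error.** With an assumed utility SD of 0.10-0.20 and clustering ignored, the standard error of the difference is SD × √(2/172) = 0.011-0.022. One excess death therefore moves the estimate by about 0.2-0.4 standard errors.

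**The case against.** The strongest reply is that this is a narrow gap in an analysis the plan labels exploratory. Mortality is neither a hypothesis nor an outcome in Section II or Table 5, and the primary aim is not touched by this route. The bipolar pilot reported no suicide attempts among 457 patients, although it was short and did not report all deaths. All of this stands and limits the weight of the point.

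A second reply is that the pattern mixture model already allows for non-ignorable missingness and leaves room for a death pattern. That is fair as far as it goes: the plan does not rely on the at-random assumption alone. But the model is a sensitivity analysis, does not name death or set it to 0, and is not linked to Aim 3.

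A third is that the plan nowhere says a death will be omitted or imputed. That is correct; the consequence follows from applying the only rule given.

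A reader might also infer two stronger charges that the documents do not support:
- **That the cost handling is wrong.** Costs properly stop at death. The plan does not say whether a patient without a utility keeps their costs in the ratio, and it gives no figure for costs before a death, so lower costs in the arm with more deaths are not established.
- **That the plan departs from intent-to-treat.** C.5.g commits to it for all analyses. Silence on death is not a departure, and a mixed model or imputation can keep every patient in the assigned arm.

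**Conclusion.** The point holds for the effect side of Aim 3. Effectiveness is survey-based utility change alone, and the stated rule gives death no value, so an excess of deaths in one arm does not lower that arm's effectiveness. The direction is not fixed in advance: the omission flatters whichever arm has more deaths.

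The size is modest and rests wholly on assumed inputs. It is about 0.0035-0.0041 in mean 24-month utility per excess death, which is 9-20% of an assumed 0.02-0.04 gain at month 24, or roughly 4-10% in QALYs under a sustained gain and a death at month 12. It is close to nil if deaths are equal. A small imbalance is nonetheless likely by chance alone across the assumed mortality range. The correction is standard and nearly free, so it is worth making even in an exploratory analysis, and before results by arm are seen.

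**What to change.** In the Aim 3 paragraph of C.5.g, state that:
- utility is 0 from the date of death to month 24, and deaths are not imputed under the at-random model;
- patients who die stay in both the cost and the effect side of every bootstrap resample;
- death is flagged separately from plan disenrolment and from loss to follow-up;
- deaths are reported by arm.

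Ascertain vital status in the same way in both arms, from sources the trial already has: plan records, the six-monthly survey contact attempts and adverse event reports. This matters because CCM patients also receive monthly calls (Table 4) and EC patients do not. If those calls revealed deaths that would be missed in EC, scoring only known deaths as 0 would bias the comparison against CCM.

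The cost is a few sentences and one derived variable. The zeros will slightly widen the interval for the utility difference. The plan does not say that its records capture vital status, and deaths after disenrolment may be missed; this should be stated as a limitation.

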### **III. Background and Significance**

#### **A. Significance.**

##### **1. Majority of care for mental disorders is provided by private solo or small practices.**

The 2011 HHS report on multiple chronic conditions (1) highlighted the prevalence, morbidity, and cost associated with clusters of co-occurring chronic conditions, and lack of current treatment strategies. A recently completed AHRQ report (2) and meta-analysis by our group (3) concluded that collaborative chronic care models (**CCMs**) are effective in treating chronic medical and mental illnesses at little to no net healthcare cost (4-6). CCMs consist of: (a) patient self-management skill enhancement, (b) expert decision support to providers via evidence-based practice guidelines, and (c) enhanced access and continuity via care managers working in collaboration with physicians to support information flow between patients and providers (7, 8).

Our recent meta-analysis of CCMs also found that they have primarily been implemented at the facility level in publically funded settings (2, 3, 9, 10). Still, between 50-70% of patients with mental health conditions are managed by commercial health plans (11). Moreover, in a recent analysis we have also determined that 85% of those with mood disorders receive care from solo or small practices (12) that are less likely to be able to implement care management processes at the practice level (13).

CCMs will become increasingly important as healthcare delivery systems evolve into accountable care organizations (14, 15), thereby taking on broader responsibility for care coordination and quality while bearing financial risk for complex, chronic conditions. CCMs can provide either the foundation of, or an annex to, emerging medical home methodologies (16-18). However, dissemination of CCMs is limited to larger practice venues with sufficient infrastructure (19, 20). To date CCMs for chronic disorders have been implemented as clinic-based interventions (21) or within integrated healthcare systems, but not in smaller practices (22).

